#### 9.2.4. Serious Adverse Events

#### **Serious Adverse Event (SAE):**

An AE or suspected AE is considered "serious" if, in the view of either the investigator or sponsor, it results in any of the following outcomes:

- death,
- a life-threatening AE,
- inpatient hospitalization or prolongation of existing hospitalization,
- a persistent or significant incapacity or substantial disruption of the ability to conduct normal life functions, or
- a congenital anomaly/birth defect.
- Important medical events that may not result in death, be life-threatening, or require hospitalization may be considered serious when, based upon appropriate medical judgment, they may jeopardize the subject and may require medical or surgical intervention to prevent one of the outcomes listed in this definition. Examples of such medical events include allergic bronchospasm requiring intensive treatment in an emergency room or at home, blood dyscrasias or convulsions that do not result in inpatient hospitalization, or development of drug dependency or drug abuse.

#### SAEs will be:

- Assessed for severity and relationship to study drug and alternate etiology,
- Recorded on the appropriate SAE data collection form and eCRF,

<sup>1 An AE is considered "life-threatening" if, in the view of either the site PI/designee or sponsor, its occurrence places the subject at immediate risk of death. It does not include an AE, had it occurred in a more severe form, might have caused death.

- Followed through resolution,
- Reviewed and evaluated by the DSMB (periodic review unless related), DMID, and IRB/IEC.

SAEs are only recorded in subjects receiving at least two doses of fosfomycin.

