## 9. ASSESSMENT OF SAFETY

## 9.1. Specification of Safety Parameters

Safety will be assessed by the frequency and severity of AEs, AESIs, and SAEs.

Levofloxacin, Cefixime, Amoxicillin and clavulanate, and Trimethoprim-sulfamethoxazole are FDA-approved drugs for the treatment of UTI with established and well-described safety profile and NIAID does not expect that any new drug related safety signal will be detected in this trial. As such, the safety data collection will be targeted to collect Suspected Unexpected Serious Adverse Reaction (SUSAR) for all agents, grade 2 and above solicited adverse events and AESIs as specified in this protocol and grade 2 and above unsolicited adverse events and SAEs only for subjects taking 2 or more doses of fosfomycin

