# 9.2. Methods and Timing for Assessing, Recording, and Analyzing Safety Parameters

Any deaths, any related SAEs, and AESIs will be sent to the SMC DSMB chair for review within two business days of the DMID's Medical Monitor assessment.

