## 9.3. Reporting Procedures

#### 9.3.1. Serious Adverse Events

SAEs will be followed until resolution even if this extends beyond the study's reporting period. Resolution of an AE is defined as the return to pretreatment status or stabilization of the condition with the expectation that it will remain chronic.

Any AE that meets a protocol-defined serious criterion must be submitted immediately (within 24 hours of site awareness) on an SAE form to the DMID Pharmacovigilance Group:

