## 9.5. Halting Rules

### Study Halting Rules

If any of the halting rules, as outlined below, is met, further enrollment will be withheld until the DSMB reviews the safety data and provides its recommendations. The continuation of the administration of study drugs (continue the current antibiotic or switch to other one) will be at the PI discretion.

- Any death reported across the pooled study strategies, related to the treatment of fosfomycin.
- If >2 related SAEs in the same high level group term (HLGT) that are observed in subjects who take more than 1 dose of study prescribed fosfomycin, not including *Clostridioides difficile*.
- If ≥5 AESIs are observed across the pooled study strategies (≥5% if more than 100 subjects enrolled)

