## 11.4. Final Analysis Plan

Planned analyses of all primary and secondary endpoints will be described in detail in the SAP to be prepared by the DCC and finalized prior to unblinding of the study data.

The primary analysis will be a superiority analysis of treatment success at TOC by study arm in the micro-ITT analysis population. Multiple imputation will be used in the case of missing values for treatment success at TOC in the micro-ITT population. The test of the null hypothesis of no difference between the strategies for the primary outcome (Section 11.1) will be performed using linear regression, and will include site, pyelonephritis, and number of bacterial species detected in the urine at baseline as covariates. Further details of the analysis, including the multiple imputation model, will be described thoroughly in the SAP. As a secondary analysis, a difference in treatment success at EOT by treatment strategy will be tested in the micro-ITT population, using methods analogous to the primary analysis. Sensitivity analyses will be performed for the primary analysis including a complete case analysis in which subjects are analyzed as randomized without imputation and tipping point analyses.

The safety analysis population will include all subjects receiving at least one dose of study drug. 95% confidence intervals of frequencies of solicited and unsolicited adverse events, SAEs and AESIs will be provided using the Wilson score method.

Frequency and number of solicited adverse events of grade 2 and above will be reported by treatment arm, study day, and severity, and differences between treatment arms in frequency of grade 2 and above severity solicited adverse events after the first dose of study drug will be tested using Fisher Exact Tests. For subjects receiving fosfomycin, frequency and number of each solicited adverse event of grade 2 and above severity occurring any time from date of first dose of fosfomycin in subjects receiving 2 or more doses until 2 days after last dose of fosfomycin will be tabulated.

Frequency and number of SAEs in subjects receiving at least two doses of fosfomycin during the trial will be tabulated.

For subjects receiving fosfomycin, frequency of each unsolicited adverse event of grade 2 and above severity occurring in subjects receiving at least two doses of fosfomycin until 2 days after last dose of fosfomycin will be tabulated overall and by MedDRA® System Organ Class and Preferred Term.

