- g. An adequate and appropriate infection specimen should be obtained at the specified time points. If a subject fails treatment at any point in this study, an adequate and appropriate specimen should be obtained. The microorganisms identified from the urine culture will be sent to central study laboratory for susceptibility testing.
- h. Unsolicited grade 2 and above AEs and SAEs will be recorded in subjects receiving at least 2 doses of fosfomycin. A follow up visit on Day 7-14 is done by phone and only for a subject which last dose of oral antibiotic per protocol was fosfomycin.
- i. Review urine culture results if available
- j. Review urine culture results if not available at screening/randomization

DMID/NIAID/NIH 90

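### SAE recording is limited to subjects with at least two fosfomycin doses; this conflicts with the protocol's other SAE, SUSAR and death rules and makes SAE counts by strategy non-comparable

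*Protocol*

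**What the plan says.** The restriction appears in three places in the protocol. Section 9.2.4 says "SAEs are only recorded in subjects receiving at least two doses of fosfomycin". Section 9.1 limits collection to "grade 2 and above unsolicited adverse events and SAEs only for subjects taking 2 or more doses of fosfomycin". Appendix A footnote h says "Unsolicited grade 2 and above AEs and SAEs will be recorded in subjects receiving at least 2 doses of fosfomycin". The note under SAP Table 34 repeats it. Section 9.1 explains the choice: levofloxacin, cefixime, amoxicillin-clavulanate and TMP-SMX are approved drugs whose safety is already well described.

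Other protocol passages carry no such limit:

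- 9.3.1: "Any AE that meets a protocol-defined serious criterion must be submitted immediately (within 24 hours of site awareness) on an SAE form".
- 9.2: "Any deaths, any related SAEs, and AESIs will be sent to the SMC DSMB chair for review".
- 9.1, in the same sentence as the restriction: "the safety data collection will be targeted to collect Suspected Unexpected Serious Adverse Reaction (SUSAR) for all agents".
- 9.5, first halting rule: "Any death reported across the pooled study strategies, related to the treatment of fosfomycin".

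Section 11.4 defines a safety population of anyone with at least one dose of study drug, then promises that "95% confidence intervals of frequencies of solicited and unsolicited adverse events, SAEs and AESIs will be provided using the Wilson score method". Later in the same section, SAEs are to be tabulated in subjects with two or more fosfomycin doses.

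**The concern.** A site faced with a serious event in a subject who has had fewer than two fosfomycin doses cannot tell whether an SAE record is required: 9.2.4 says no and 9.3.1 says yes. Two consequences follow.

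The first concerns oversight of the investigational drug. If a serious reaction to the first fosfomycin dose prevents a second, the event itself takes the subject out of the recorded set. The rule then selects on the outcome it is meant to count. Protocol 2.3.1 lists anaphylaxis and angioedema among rare serious events reported with fosfomycin, so this is not a remote category.

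The second concerns the comparison. The overall objective in 3.1 covers safety as well as efficacy. Whether an SAE is recorded depends on fosfomycin exposure after randomisation, which differs between the arms by design.

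**Working it through.** No figure in the plan is in dispute. The check is to apply each rule to the same four cases.

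| Case | 9.2.4, 9.1, footnote h | Other rules |
|---|---|---|
| A. One fosfomycin dose, serious event, no second dose | Not recorded | 9.3.1: submit within 24 hours. 9.2: refer if related or fatal. 9.1: collect if a SUSAR. 9.5: first halting rule met if fatal and related |
| B. Strategy 2, levofloxacin only, non-fatal serious event that is unrelated or expected | Not recorded | 9.3.1: submit within 24 hours. 9.2: refer if related. Not a SUSAR |
| C. Same event as B, Strategy 1, two or more fosfomycin doses | Recorded | 9.3.1: submit within 24 hours |
| D. Event after fosfomycin dose 1 in a subject who goes on to dose 2 | Not clearly excluded | 9.3.1: submit within 24 hours |

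Case A shows the conflict at its sharpest. A fatal reaction to a first fosfomycin dose would meet the first halting rule, yet the subject is outside SAE recording. A SUSAR is by definition a serious event, so collecting SUSARs on all agents means that serious events on all agents must first be captured and assessed. The rationale in 9.1 names only the comparators and does not speak to case A.

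Cases B and C are the same event, counted in one arm and not in the other.

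Case D marks the limit of the point. Section 9.2.4 sets a condition on the subject and gives no start time. The start at the second dose in 9.2.3 is written for unsolicited AEs.

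**How much of Strategy 2 is covered (illustration).** Inputs:

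- Planned subjects per arm: 634 / 2 = 317 (Protocol 11.2, 1:1 allocation).
- Levofloxacin non-susceptibility: 10–30%, borrowed from the US fluoroquinolone-resistance range in Protocol 2.1.
- Share of those subjects switched to fosfomycin and taking at least two doses: 25–100%. This is an assumption; the documents give no figure.

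Covered subjects = 317 × resistance × share switched:

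- Low: 317 × 0.10 × 0.25 = 7.9; fraction outside = 1 − 0.025 = 97.5%.
- High: 317 × 0.30 × 1.00 = 95.1; fraction outside = 1 − 0.30 = 70%.

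With the 62 subjects enrolled and an even split assumed (31 per arm), the same fractions give 31 × 0.025 = 0.8 to 31 × 0.30 = 9.3 covered Strategy 2 subjects. Switches for intolerance or quinolone risk would raise coverage somewhat.

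**Display.** SAP Tables 34 and 35 show SAEs in Strategy 1 and Strategy 2 columns within the Fosfomycin Safety Population. Under the treatment plan, the Strategy 2 column can hold only subjects adjusted to fosfomycin.

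**The case against.** The best defence is that this is a deliberate, reasoned choice, stated consistently. The secondary SAE outcome in 3.2.2 is a count in subjects with two or more fosfomycin doses. Section 11.4 tabulates SAEs in that group, the second halting rule uses the same threshold, and the SAP has a dedicated population for it. The note under SAP Table 34 discloses the limit. That defence stands for the comparators as a data-collection choice. It also means that the Wilson-interval sentence in 11.4 leaves the SAE denominator unstated rather than contradicting the limit outright. It does not resolve the conflict with 9.3.1, 9.2, the SUSAR clause or the first halting rule, and it gives no reason for leaving out one-dose fosfomycin subjects.

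Four stronger readings are tempting, and the documents do not support them.

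- A reader might infer that every serious event after a first fosfomycin dose goes unrecorded. Case D shows otherwise.
- A reader might infer that nothing serious is captured on levofloxacin. SUSARs, AESIs and grade 2 and above solicited AEs are collected without a fosfomycin condition, 9.2 refers deaths and related SAEs, SAP 7.1 lists reasons for early termination including death, and switched subjects are covered. What is lost is mainly expected or unrelated SAEs. Section 9.3.2 confines IND reporting to fosfomycin, so it creates no separate duty for levofloxacin.
- A reader might infer that a planned analysis fails. The between-strategy AE comparison in 3.1.2 is of solicited events, collected in both arms; no SAE comparison is pre-specified.
- A reader might want a count of missed SAEs per arm. The documents give no SAE rate on which to base one.

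It is also fair to say that the trial has closed, so amending the protocol cannot recover data.

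**Conclusion.** The concern holds in a limited form. The passages on who has SAEs recorded and reported are inconsistent and must be reconciled. Apart from SUSARs and AESIs, the gap consists of fosfomycin subjects stopped by a serious event after exactly one dose, and Strategy 2 subjects who never reach two fosfomycin doses. On the assumptions shown, the second group is 70–97.5% of the Strategy 2 arm; the size of the first cannot be derived from the documents. SAE counts by strategy are conditioned on exposure after randomisation and cannot serve as a randomised comparison. That is a limitation against the general safety objective, not the loss of a planned test. The change should be made.

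**What to change.** **Protocol text.** Reconcile 9.1, 9.2, 9.2.4, 9.3.1, 9.5, 11.4 and Appendix A footnote h so that SAEs are recorded in every subject who receives at least one dose of study drug, through TOC. State in 11.4 which denominator the SAE frequencies and their intervals use.

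**Closed trial.** Three steps remain useful:

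1. List the deaths and serious events known in all treated subjects from the data already held, such as disposition, early-termination, unscheduled-visit and AESI records. Present this as a listing of known events, not as rates: AESI review covers only two diagnoses, so the list will be incomplete.
2. Label the Strategy 2 columns of SAP Tables 34 and 35 as containing only subjects switched to fosfomycin.
3. State in the CSR and the manuscript that SAEs were not systematically collected in subjects with fewer than two fosfomycin doses. SAP Section 12 does not mention this at present.

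**Cost.** A small number of additional SAE forms, since Appendix A already schedules SAE collection from the randomisation visit through TOC. For the closed trial, the cost is one listing, revised column labels and a sentence in each report.

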# 9.2.5. Procedures to be Followed in the Event of Abnormal Laboratory Test Values or Abnormal Clinical Findings

Serum chemistries including Cr, BUN, glucose, sodium, potassium, chloride, bicarbonate, calcium and liver function tests (AST, ALT, alkaline phosphatase, total bilirubin) and hematology including complete blood count (with RBC count, hemoglobin, hematocrit, total WBC count with differential counts, and platelet count), will be ordered at the screening visit if not already done as standard of care.

Regular safety laboratory tests will not be ordered.

## 9.2.6. Adverse Events of Special Interest

AESIs are diagnoses that were retrieved by record review if a subject had an unexpected clinical encounter during the follow-up period (up to 28 days), and include the following

- Clostridioides difficile infection, as defined by ≥3 unformed stools (soft or watery) within 24 consecutive hours with a positive test for Clostridioides difficile
- Altered cardiac conduction, as defined by dysrhythmia different from subject's previously documented rhythm or a prolongation of any ECG interval by >25% from subject's previously documented ECG intervals. If no prior ECG is available for comparison, then a QTc >470 ms for men and >480 ms for women will be deemed abnormal and documented as an AESI.

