#### Levofloxacin

Levofloxacin has been licensed in the US since 1996 and is currently used as first-line therapy for cUTI. However, the FDA recently warned that "serious side effects associated with fluoroquinolone antibacterial drugs generally outweigh the benefits for patients with acute sinusitis, acute bronchitis, and uncomplicated urinary tract infections who have other treatment options." These include tendinopathy and tendon rupture, aortic dissection or rupture exacerbation of myasthenia gravis, hypersensitivity reactions, hepatotoxicity, central nervous system effects (with convulsions, toxic psychoses, increased intracranial pressure), peripheral neuropathy, CDAD, prolongation of the QT interval, dysglycemia, photosensitivity or phototoxicity, and development of drug-resistant bacteria.

Clinical trials experience: The following drug-related AEs were reported in >1% of individuals:

Table 2: Drug-Related Adverse Events (%) for Levofloxacin

| System/Organ Class                                  | Adverse Event           | % (N=7537)       |
|---|-------------------------|------------------|
| Infections and Infestations                         | Moniliasis              | 1                |
| Psychiatric Disorders                               | Insomnia                | 4                |
| Nervous System Disorders                            | Headache                | 6                |
|   | Dizziness               | 3                |
| Respiratory, Thoracic, and
Mediastinal Disorders | Dyspnea                 | 1                |
| Gastrointestinal Disorders                          | Nausea                  | 7                |
|   | Diarrhea                | 5                |
|   | Constipation            | 3                |
|   | Abdominal pain          | 2                |
|   | Vomiting                | 2                |
|   | Dyspepsia               | 2                |
| Skin and Subcutaneous Tissue                        | Rash                    | 2                |
| Disorders   | Pruritus                | 1                |
| Reproductive System and Breast
Disorders         | Vaginitis               | 1 (N=3758 women) |
| General Disorders and                               | Edema                   | 1                |
| Administration Site Conditions                      | Injection site reaction | 1                |
|   | Chest pain              | 1                |

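### Protocol 9.2.6 applies its QTc limit only when no prior ECG exists, so QT prolongation without a new dysrhythmia can face a higher bar in subjects who have one; the 25% rule also leaves its intervals undefined

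*Protocol*

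**What the plan says.** Protocol 9.2.6 lists altered cardiac conduction as one of two AESIs. When an earlier ECG is on file there are two routes to an event:

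- "dysrhythmia different from subject's previously documented rhythm"; or
- "a prolongation of any ECG interval by >25" per cent, measured against the intervals on the subject's earlier ECG.

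The absolute limit has its own condition: "If no prior ECG is available for comparison, then a QTc >470 ms for men and >480 ms for women will be deemed abnormal". The section does not say which intervals the 25% refers to, whether QT is rate-corrected, by which formula, or which earlier ECG is the reference.

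On capture, the same section states: "AESIs are diagnoses that were retrieved by record review if a subject had an unexpected clinical encounter during the follow-up period". Appendix A schedules no ECG. Table 5 grades arrhythmia by symptoms and intervention and contains no QTc value. SAP Table 4 repeats that scale, and the SAP adds no QTc rule of its own. AESIs of any grade are reported (SAP 4.5). They appear as one row by strategy in SAP Table 36 and are listed in SAP Table 50.

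Protocol 2.3.1 names "prolongation of the QT interval" among the serious fluoroquinolone risks.

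**The concern.** An earlier ECG should help to identify a change. Here its presence removes the QTc limit and leaves a relative rule that, for many plausible prior values, is harder to meet. A tracing that the protocol itself deems abnormal can go uncounted because an old ECG happens to be in the chart.

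The open phrase about any interval raises the opposite problem. RR and uncorrected QT both lengthen as heart rate falls, so a literal reading could score recovery from tachycardia as a conduction event.

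Other capture routes are narrow. Serious and unsolicited adverse events are recorded only in subjects with at least two fosfomycin doses (Protocol 9.2.3, 9.2.4). The solicited list in Protocol Table 4 has no cardiac item. Suspected unexpected serious reactions are collected for all agents (Protocol 9.1), but QT prolongation is a listed levofloxacin risk and would not readily qualify as unexpected. For a subject who took only levofloxacin, the AESI is the main route by which a QT finding enters the safety data.

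**Working it through.** The plan states no figure to reproduce. The check is arithmetic on the protocol's thresholds.

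**Inputs from Protocol 9.2.6:** relative rule >25%; absolute limits >470 ms (men) and >480 ms (women), used only without a prior ECG. **Assumed for illustration:** prior QTc values and heart rates, since the documents give none.

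**Step 1: where the two rules meet.** Prior QTc at which the 25% rule equals the absolute limit = limit / 1.25.

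- Men: 470 / 1.25 = 376 ms.
- Women: 480 / 1.25 = 384 ms.

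Above these values the subject with a prior ECG faces the higher bar; below them, the lower one.

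**Step 2: size of the gap.** QTc that must be exceeded = 1.25 × prior QTc.

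| Prior QTc (ms) | Must exceed (ms) | Against 470 (men) | Against 480 (women) |
|---|---|---|---|
| 380 | 475 | +5 | −5 |
| 400 | 500 | +30 | +20 |
| 420 | 525 | +55 | +45 |
| 440 | 550 | +80 | +70 |

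Worked case: a man goes from 400 to 495 ms. The rise is 95 / 400 = 23.75%, so he is not counted unless he has a new dysrhythmia or another interval has lengthened by more than 25%. With no prior ECG, 495 > 470 and he is counted. At unchanged heart rate, raw QT and QTc rise by the same percentage, so this result does not depend on whether the 25% limb means QT or QTc.

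**Step 3: the undefined interval.** For heart rate falling from h0 to h1:

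- RR ratio = h0 / h1. It passes 1.25 once the rate falls by more than 1 − 1/1.25 = 20%. For 110 to 80, 110/80 = 1.375, or +37.5%.
- Raw QT ratio at unchanged QTc = (h0/h1)^(1/2) under Bazett. It passes 1.25 once the rate falls by more than 1 − 1/1.25² = 36%.
- Under Fridericia the exponent is 1/3, and the fall must exceed 1 − 1/1.25³ = 48.8%.

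| Heart rate change (beats/min) | RR | Raw QT, Bazett | Raw QT, Fridericia |
|---|---|---|---|
| 110 to 80 | +37.5% | +17.3% | +11.2% |
| 110 to 70 | +57.1% | +25.4% | +16.3% |
| 120 to 70 | +71.4% | +30.9% | +19.7% |
| 120 to 60 | +100.0% | +41.4% | +26.0% |

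RR crosses 25% with a modest fall. Raw QT does so only with larger falls, and the answer can turn on a formula that the protocol does not name.

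**The case against.** A relative rule where a baseline exists, with an absolute fallback where none does, is a recognisable design. The first limb also matters: QT prolongation that produces a new dysrhythmia is counted whatever the percentage. A reader might infer that marked QT prolongation is missed altogether. The text does not support that; the gap is prolongation of 25% or less without a new rhythm.

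A reader might also infer that recovery from tachycardia will be scored routinely. That depends on treating RR, a measure of rate, as a conduction interval, or on raw QT and a large fall in rate. It also needs a reference ECG taken during tachycardia. Because the section calls AESIs diagnoses found after an unexpected encounter, many sites would not record a settling pulse. This half of the point is an ambiguity in wording.

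The practical effect is limited. No ECG is scheduled, enrolment ended at 62 subjects (SAP 4.1), and Table 36 is descriptive, with a single AESI row that also includes *C. difficile* infection. None of SAP Listings 1 to 24 holds ECG data, so a changed definition cannot be applied from the planned outputs alone.

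These arguments reduce the expected number of affected events. They do not explain why a QTc deemed abnormal without a prior ECG should cease to count when the prior one was lower and within the limit.

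**Conclusion.** The inconsistency stands on the protocol's own limits and needs no outside standard. For QT prolongation without a new dysrhythmia, the rule is laxer with a prior ECG whenever the prior QTc exceeds 376 ms (men) or 384 ms (women). At prior values of 400 to 440 ms the gap is 30 to 80 ms in men and 20 to 70 ms in women. The lack of named intervals and of a rate correction is a separate, lesser defect.

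The consequence is mainly for subjects with fewer than two fosfomycin doses, who have no serious-event or unsolicited-event record behind the AESI. The expected number of events is small. How many subjects had a prior ECG, and at what QTc, cannot be estimated from the documents.

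Two stronger inferences are not supported. First, bias by arm is not built in: the rule is the same for both strategies, and whether an old ECG is on file is settled before randomization. Second, a reader might infer that the halting rule based on pooled AESIs was affected, because the same count feeds it. SAP 6.6 reports that no halting rule was met, and the documents give no AESI count from which to argue otherwise.

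**What to change.** Reconcile the two limbs in Protocol 9.2.6:

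- Apply the existing QTc limits also to subjects with a prior ECG, when the limit is newly exceeded (prior QTc at or below it, on-study QTc above it).
- Keep the dysrhythmia limb and the 25% limb.
- State that the 25% limb refers to PR, QRS and rate-corrected QT, and name the correction formula and the reference ECG.

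Because enrolment has closed, the working change is in how AESIs are derived for SAP Tables 36 and 50. Apply the reconciled definition to the ECG reports already retrieved by record review, and disclose any reclassification in the abbreviated clinical study report, where the SAP Preface already requires deviations to be described.

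No new ECGs are needed. The cost is some re-review of source records, since the SAP lists no ECG values, and a few more QTc events in the tables. Some may be minor: a man moving from 469 to 471 ms would count.
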